7.6.7	Subgroup Analysis.....	35
7.7	Safety	36
7.7.1	Adverse Events	36
7.7.2	Laboratory Evaluations	38
7.7.3	Antibody Test.....	39
7.7.4	Vital Signs	39
7.7.5	Electrocardiograms	40
7.7.6	Other Safety Variables.....	40
7.8	Primary Analysis of the Study	40
8	CHANGES IN PLANNED ANALYSES	40
9	DATA ISSUES.....	40
10	REFERENCES	40
11	CCI [REDACTED]	
	[REDACTED]	
	[REDACTED]	
	[REDACTED]	
	[REDACTED]	
	[REDACTED]	
	[REDACTED]	
	[REDACTED]	
	[REDACTED]	
	[REDACTED]	
	[REDACTED]	

Statistical Analysis Plan

Version: Final v2.0

September-2018

Ipsen Protocol No. D-FR-52120-222

000000146259

Date of Issue: 21-

Covance Study ID:

GLOSSARY OF ABBREVIATIONS

Abbreviation	Term
AE	Adverse event
AESI	Adverse events of special interest
ANCOVA	Analysis of Covariance
ASIA	American Spinal Injury Association
ATC	Anatomical Therapeutic Chemical
BMI	Body mass index
BTX	Botulinum Toxin
BTX-A	Botulinum Toxin Type A
CHMP	Committee for Medicinal Products for Human Use
CI	Confidence Interval
CIC	Clean intermittent catheterisation
Cm	centimetre
CS	Compound symmetry
CSR	Clinical Study Report
DBPC	Double-blind placebo-controlled
DC	Detrusor compliance
ECG	Electrocardiogram
EFP	End fill pressure
EOS	End of study
EQ-5D-5L	EuroQol 5-dimension 5-level
eCRF	Electronic Case Report Form
FDA	Food and Drug Administration
GLMM	Generalised Linear Mixed Model
Ho	Null hypothesis
Ha	Alternative hypothesis
ICH	International Conference on Harmonisation
IDC	Involuntary detrusor contraction
IMP	Investigational medicinal product
I-QoL	Incontinence quality of life
IVRS	Interactive Voice Response System
Kg	kilogram
LOCF	Last observation carried forward
LPLV	Last patient last visit
LSMEANS	Least square means
n	Number of subjects
NA	Not applicable
MAR	Missing at random
MCC	Maximum cystometric capacity
MDP	Maximum detrusor pressure
MedDRA	Medical Dictionary for Regulatory Activities
MI	Multiple Imputation
MMRM	Mixed model repeated measures
mPGI-I	Modified patient global impression – improvement
mITT:	Modified Intention-To-Treat
MS	Multiple sclerosis
NDO	Neurogenic detrusor overactivity
PdetMax@1stIDC	Maximum detrusor pressure at first involuntary detrusor contraction
PP	Per-protocol
PT	Preferred Term

Statistical Analysis Plan

Version:Final v2.0

September-2018

Ipsen Protocol No. D-FR-52120-222

000000146259

Date of Issue: 21-

Covance Study ID:

SAE	Serious Adverse Event
SAP	Statistical Analysis Plan
SAS®	Statistical Analysis System®
SCI	Spinal Cord Injury
SD	Standard Deviation
SMQ	Standardised MedDRA Query
SOC	System Organ Class
TEAE	Treatment Emergent Adverse Event
TFLs	Tables, Figures and Listings
U	Units
UTI	Urinary tract infection
UI	Urinary incontinence
VC	Variance components
vs	Versus
Vol@1stIDC	Volume at first involuntary detrusor contraction
WHO	World Health Organisation

Statistical Analysis Plan

Version: Final v2.0
September-2018
Ipsen Protocol No. D-FR-52120-222
000000146259

Date of Issue: 21-
Covance Study ID:

1 SOURCE DOCUMENTS

This statistical analysis plan (SAP) Final v2.0 has been developed to supplement the statistical analysis described in the Final SAP (dated 8th March 2018) and clinical trial protocol amendment (D-FR-52120-222, dated 16th April 2018).

This SAP Final v2.0 describes the methodology and considerations of the planned analyses and a list of all the tables, figures and listings (TFLs) for this study. A detailed description of the planned TFLs will be provided in a separate TFLs shell document. Any minor changes to the TFL shells including but not limited to changes in TFL numbering, TFL footnotes or to the title of the TFLs will not require a revision to this SAP Final v2.0. Any major changes to the TFL shells or SAP Final v2.0 text may result in a revised amendment to this SAP.

This SAP and any amendments will be finalized prior to the lock of the clinical database. Any changes to the analyses described in this document or additional analyses performed to supplement the planned analyses will be described in the clinical study report (CSR).

The SAP was written based on the following documentation:

- International Council on Harmonisation (ICH) E9 guideline entitled, “Guidance for Industry: Statistical Principles for Clinical Trials” (ICH Guideline E9 1998)
- ICH E3 guideline entitled, “Guidance for Industry: Structure and Content of Clinical Study Reports” (ICH Guideline E3 1996)

Document	Date	Version
Protocol	14 September 2015	Final 1.0
Protocol Amendment 1	16 April 2018	Final 2.0
CCI [REDACTED]	19 September 2017	
eCRF	06 December 2016	Final 2.0
Data Model Specification for CRF Health	17 February 2016	Version 2
Trial Manager Tailoring Specification for CRF Health	23 May 2016	Version 4
I-QOL User Manual	March 2013	US English
Bladder Diary Terminology Document	07 April 2017	Version 3
EQ-5D-5L User Guide	April 2015	Version 2.1

2 PROTOCOL DETAILS

2.1 Study Objectives

Primary Study Objective:

- To assess the efficacy of two Dysport doses (600 units [U] and 800 U), compared to placebo in reducing urinary incontinence (UI) from Baseline to Week 6 following the first investigational medicinal product (IMP) administration.

Secondary Study Objectives:

- To assess the efficacy of two Dysport doses (600 U and 800 U), compared to placebo in improving bladder diary measures, urodynamic and patient-reported efficacy endpoints following the first IMP administration, including assessing duration of effect.

Statistical Analysis Plan

Version: Final v2.0

September-2018

Ipsen Protocol No. D-FR-52120-222

000000146259

Date of Issue: 21-

Covance Study ID:

- To assess the efficacy of two Dysport doses (600 U and 800 U) in improving bladder diary measures and patient-reported efficacy endpoints following retreatment IMP administrations, including assessing duration of effect.
- To assess the safety of two Dysport doses (600 U and 800 U) for the treatment of UI due to neurogenic detrusor overactivity (NDO).

2.2 Overall Study Design

This is a Phase III, multicenter, randomised, double-blind, parallel group, placebo controlled study to assess the efficacy and safety of two Dysport doses (600 U and 800 U) administered to the bladder of adult subjects with NDO due to spinal cord injury (SCI) or multiple sclerosis (MS).

The target population is subjects with UI caused by NDO due to either SCI or MS, who have not been adequately managed with oral medication and who routinely require clean intermittent catheterisation (CIC) to manage their bladder function.

The study will include two treatment periods.

- A double-blind placebo controlled (DBPC) treatment, i.e. following Treatment 1 on Day 1 during which subjects receive a single IMP treatment administration of either
 - Dysport 600 U
 - Dysport 800 U
 - Placebo.DBPC Cycle will run from randomisation and treatment on Day 1 to the administration of Treatment 2. The length of the DBPC period will depend on when the patient receives Treatment 2.
- A subsequent double-blind active treatment period, during which subjects can receive multiple active IMP retreatment administrations of either;
 - Dysport 600 U
 - Dysport 800 U.

Subjects who were randomised to receive Dysport at Treatment 1 (600 U or 800 U) will continue to receive the same dose for all subsequent treatments and those who were initially randomised to placebo will receive either 600 U or 800 U, depending on their allocated randomisation sequence (see next section).

Screening

Screening period will last for up to 30 days, but can be extended in certain circumstances to obtain an appropriately and fully completed bladder diary or to obtain a valid bladder diary. Furthermore, where a urinary tract infection (UTI) occurs after completion of the bladder diary and impacts the ability to perform urodynamics, the time to Screening Visit 2 can be extended until the UTI is resolved. During the screening period, informed consent will be obtained and eligibility for study participation will be assessed. Subjects will complete a 7-day bladder diary, urodynamic assessment, patient-reported outcome questionnaires and have blood and urine samples taken.

Randomisation/treatment

The Treatment Visit (Day 1) should occur up to 14 days after the screening period, but can be extended until the UTI is resolved (where a UTI has occurred and impacts the ability to perform IMP administration). At the Treatment 1 visit on Day 1, subjects who meet all the eligibility criteria will be randomised (in a 2:2:1:1 ratio) to one of four treatment sequences:

Statistical Analysis Plan

Version: Final v2.0

September-2018

Ipsen Protocol No. D-FR-52120-222

000000146259

Date of Issue: 21-

Covance Study ID:

Sequence	Subjects	1 st Treatment in DBPC Cycle	Subsequent retreatment(s) in Dysport Cycles (Dysport Cycle 1, Dysport Cycle 2, etc)
1	110 subjects	Dysport 600 U	Dysport 600 U
2	110 subjects	Dysport 800 U	Dysport 800 U
3	55 subjects	Placebo	Dysport 600 U
4	55 subjects	Placebo	Dysport 800 U

During the analysis of DBPC cycle, the two placebo containing sequences will be pooled into a single arm.

Randomisation will be stratified by;

- Aetiology of NDO (SCI or MS)
- Previous intradetrusor botulinum toxin type A (BTX-A) usage (BTX-A naïve vs. BTX-A non-naïve).

Follow-up (after IMP administration in DBPC cycle):

- Week 1 (Day 8) (telephone)
- Week 2 (Day 15) (clinic visit)
- Week 4 (Day 29) (telephone)
- Week 6 (Day 43) (clinic visit; primary timepoint)
- Week 12 (Day 85) (clinic visit; the retreatment could be requested by subject from this visit)
- Every 12 weeks (telephone visits; until retreatment received or end of study (EOS) at Weeks 104 to 116).

Details of the procedures performed at each visit following the first treatment are shown in the schedule of assessments, [Appendix V](#).

Retreatment assessment

A subject may request retreatment with IMP at any time ≥ 12 weeks after their most recent study treatment.

The retreatment criteria are as follows:

- 1) Retreatment requested by subject;
- 2) More than 12 weeks (84 days) since the previous IMP administration;
- 3) CCI [REDACTED]
- 4) [REDACTED]
- 5) In the investigator's opinion it is safe and appropriate to provide retreatment.

Statistical Analysis Plan

Version: Final v2.0

September-2018

Ipsen Protocol No. D-FR-52120-222

000000146259

Date of Issue: 21-

Covance Study ID:

A patient may only be retreated if eligible based on the study retreatment criteria. The bladder diary device/portal may provide an indication that the patient is within 30% of their Baseline (Screening) UI level, however to confirm eligibility a manual calculation can be performed by multiplying the weekly number of UI episodes on the screening bladder diary by 0.7. If the subject has a current number of weekly UI episodes greater than this calculated number then the subject is within 30% of their Baseline UI level and meets the retreatment criterion #3.

Example calculation:

- Study Baseline (Screening) number of weekly UI episodes = 28 episodes
28 episodes x 0.7 = 19.6 (rounded up to 20)
- Subject is therefore eligible for retreatment if current weekly UI episodes are 20 or more.

Retreatment should ideally occur within 14 days of confirmation of eligibility for retreatment and can occur up to and including Week 104 following the first IMP administration of the first period.

Retreatment follow-up

Follow-up after each retreatment follows the same schedule as the first IMP administration (Treatment 1).

- Week 1 (Day 8) (telephone)
- Week 2 (Day 15) (clinic visit)
- Week 4 (Day 29) (telephone)
- Week 6 (Day 43) (clinic visit)
- Week 12 (Day 85) (clinic visit; the retreatment could be requested by subject from this visit)
- Every 12 weeks (telephone visits; until retreatment received or EOS at Weeks 104 to 116).

Details of the procedures performed at each Retreatment Follow-up Visit in the Dysport cycle are contained in [Appendix V](#).

End of Study Visit

The EOS Visit will take place between 104 and 116 weeks after the first IMP administration on Day 1. Subjects may receive study retreatment up to and including Week 104 and a minimum of 12 weeks of follow-up is required after each IMP administration. For those subjects completing the study, the EOS Visit will occur:

- At Week 104 after the first IMP administration, if it has been more than 12 weeks since the previous IMP administration.
- At Week 12 Retreatment Follow-up Visit, if the subject received their most recent IMP administration between Week 92 and Week 104 following their first IMP administration.

Early discontinuation

A subject who discontinues the study early should, if at all possible, be followed-up for at least 12 weeks following their most recent IMP administration and should attend the EOS Visit.

Duration of subject participation

104 weeks (24 months) to 116 weeks depending on the timing of final IMP administration.

2.3 Sample Size and Power

The sample size is based on the ability to detect a statistically significant treatment difference in the weekly number of UI episodes at Week 6 following the first IMP administration in the two Dysport arms (600 U and 800 U) compared to the placebo arm.

Assuming a weekly decrease of 21 UI episodes in each Dysport arm and a weekly decrease of 12 UI episodes in the placebo arm, with a common standard deviation of 20 UI episodes, 80% power, and an alpha of 0.025 (as testing of both the 600 U and 800 U doses vs. the placebo dose will be performed simultaneously), a sample size of 96 subjects per dose group (a total of 288 subjects) is needed. Dropout between randomisation and Week 6 (primary efficacy timepoint) is expected to be 10%, and thus a total of 318 subjects would be needed to be enrolled. However, in order to ensure that the development program will deliver adequate Dysport exposure data to meet ICH E1 guideline recommendations, a total of 330 subjects are planned to be randomised. Subjects who leave the study early will not be replaced.

Sample size calculations were performed in SAS Studio 3.6.

3 EFFICACY AND SAFETY VARIABLES

For the purpose of all analysis, the study baseline is defined as the last value available during screening or day of treatment visit prior to the first study IMP treatment administration (Treatment 1) i.e. prior to the DBPC Cycle. This study baseline will be used in analysis of the efficacy endpoints and the safety endpoints for all treatment cycles.

3.1 Primary Efficacy Endpoint

The primary efficacy endpoint is the mean change from study baseline in weekly number of UI episodes at Week 6 after the first IMP administration (Treatment 1).

3.2 Secondary Efficacy Endpoints

The secondary efficacy endpoints are divided into those that relate to parameters measured in the bladder diary, those measured by urodynamic filling cystometry and those that are quality of life measures. From these secondary measures, there are several that have been selected to be analysed as part of a hierarchical testing scheme (for week 6 after Treatment 1) see Section 3.2.1.

Bladder diary measures:

Mean change from study baseline to post-treatment timepoints in the following variables:

- weekly number of UI episodes (except for week 6 after Treatment 1 which is the primary efficacy endpoint)
- total daily urinary frequency (spontaneous void and CIC)
- daily spontaneous voiding frequency
- daily CIC frequency
- total 24-hour voided volume (spontaneous void and CIC)

Statistical Analysis Plan

Version: Final v2.0

September-2018

Ipsen Protocol No. D-FR-52120-222

000000146259

Date of Issue: 21-

Covance Study ID:

- 24-hour voided volume (spontaneous void only)
- 24-hour voided volume (CIC only)
- total volume per void (spontaneous void and CIC)
- volume per void (spontaneous void only)
- volume per void (CIC only)

Proportion of subjects with:

- no episodes of UI (i.e. 100% improvement where continence is achieved)
- UI response at several levels (i.e. $\geq 30\%$ improvement, $\geq 50\%$ improvement, $\geq 75\%$ improvement)

Urodynamic filling cystometry measures:

Mean change from study baseline to week 6 after Treatment 1 in the following variables:

- MCC
- MDP during storage
- Vol@1stIDC (subjects without a post-treatment IDC will have their Vol@1stIDC imputed from their MCC)
- maximum detrusor pressure at first involuntary detrusor contraction (PdetMax@1stIDC)
- end fill pressure (EFP)
- detrusor compliance (DC)

Proportion of subjects with:

- No IDCs (i.e. urodynamic cure is achieved)

Patient-reported outcome questionnaires:

Mean change from study baseline to post-treatment timepoints in the following variables:

- I-QoL total summary score
- I-QoL Score of domain: Avoidance and limiting behaviour
- I-QoL Score of domain: Psychosocial impact
- I-QoL Score of domain: Social embarrassment
- EuroQol 5-dimension 5-level (EQ-5D-5L): Total descriptive score
- EQ-5D-5L: self-rated health (VAS)
- modified patient global impression - improvement (mPGI-I) score (to be assessed at each timepoint without comparison to baseline)

Duration of effect following the first and subsequent treatments

- time to request retreatment
- time to eligibility for retreatment
- time between treatments.

Detailed definitions of all efficacy endpoints are presented in [Appendix II](#).

3.2.1 Hierarchical Analysis of Selected Secondary Endpoints

A hierarchical analysis will be performed in the order listed for the following secondary efficacy endpoints at Week 6 after Treatment 1:

- 1) Mean change from study Baseline (assessed at Screening) in the MCC:
 - measured by urodynamic filling cystometry.
- 2) Mean change from study Baseline (assessed at Screening) in the MDP during storage:
 - measured by urodynamic filling cystometry.
- 3) Mean change from study Baseline (assessed at Screening) in the Vol@1stIDC:
 - measured by urodynamic filling cystometry.
- 4) Proportion of subjects with no episodes of UI (i.e. continence is achieved):
 - measured by 7-day bladder diary.
- 5) Proportion of subjects with no IDCs during storage:
 - measured by urodynamic filling cystometry.
- 6) Mean change from study Baseline (assessed at Screening) in the I-QoL total summary score:
 - measured by patient-reported questionnaire.

3.3 Safety Variables

Safety will be assessed throughout the study by evaluating:

- Treatment Emergent Adverse Events (TEAEs)
- Adverse events of special interest (AESI)
 - Adverse events (AEs) related to toxin spread
 - AEs related to hypersensitivity
- Other protocol defined TEAEs
 - Urinary Tract Infections (UTI)
- Vital signs (heart rate, respiratory rate, blood pressure and body temperature)
- Laboratory blood parameters (haematology and serum chemistry)
- Laboratory urine parameters (laboratory urinalysis/microscopy, culture and sensitivity)

- Development of BTX-A antibodies (neutralizing)
- Usage of concomitant medications and therapies.

Timepoints for safety evaluations are detailed in [Appendix V](#).

4 PHARMACOKINETIC/PHARMACODYNAMIC VARIABLES

Not applicable.

5 ANALYSIS POPULATIONS

5.1 Screened Population

Screened population includes all subjects screened (enrolled); these are subjects who have signed the informed consent.

5.2 Randomised Population

All subjects assigned a randomisation number. Randomised subjects will be analysed according to their randomised treatment.

5.3 Safety Population

All subjects who received at least one IMP administration (including only partial administration) of the IMP. Safety subjects will be analysed according to their actual treatment received.

5.4 Modified Intention-to-Treat Population

All randomised subjects who received at least one IMP administration. Modified intention-to-treat (mITT) subjects will be analysed according to randomised treatment.

5.5 Per Protocol Population

All subjects in the mITT population who have no important protocol deviations that could potentially affect the primary efficacy endpoint outcome for the subject. Per Protocol (PP) subjects will be analysed according to the randomised treatment.

5.6 Protocol Deviations

Protocol deviations are defined as any change, divergence, or departure from the study design or procedures defined in the study protocol. Important protocol deviations are a subset of protocol deviations that may significantly impact the correctness, accuracy, and/or reliability of the study data or that may significantly affect a subject's rights, safety, or well-being. A detailed list of protocol deviations that will be mapped to protocol deviation coded term based on Ipsen SDTM+ User Guide are contained in the separate document titled "Ipsen 222 and 223: Protocol Deviations"; this will be standalone working document which will be finalised prior to database lock.

5.6.1 Important Protocol Deviations Leading to Exclusion from the PP Analysis

Only those important protocol deviations considered to have a major effect on primary efficacy analysis will lead to complete exclusion of the patient from the PP population. The majority of the important protocol deviations leading to exclusion from the PP population will be determined programmatically from the data. Those criteria which require clinical or medical monitoring interpretation will be reviewed prior to database lock these will be outlined in the "Ipsen 222 and 223: Protocol Deviations" document.

5.6.2 Handling of Stratification Factors

Stratification errors (e.g. previous intradetrusor BTX-A usage) discovered after randomisation cannot be changed in the Interactive Voice Response System (IVRS) system and subjects will be analysed according to their eCRF recorded strata (i.e. correct strata) for the primary analysis of efficacy.

Mis-stratifications will be documented as a protocol deviation, and the incorrect stratification recorded in IVRS (NDO medical history for aetiology of NDO [SCI or MS], and prior medications for previous intradetrusor BTX-A usage for UI [BTX-A naïve or BTX-A non-naïve] in the bladder) will be used to perform a sensitivity analysis on the primary endpoint. A listing with the eCRF versus IVRS recorded stratifications will be displayed for the randomised subjects.

6 DATA HANDLING

6.1 Time points and Visit Windows

Day 1 is defined as the day of the first IMP administration. Relative days after Day 1 are calculated as (assessment date - Day 1 date) + 1. Relative days prior to Day 1 are calculated as (assessment date - Day 1 date). The day prior to Day 1 is Day -1.

Generally, all analysis will be performed using data at nominal visits (see Table 1). Only if the data is missing, the unscheduled visits (or early withdrawal visit) within the visit window will be used in analysis of efficacy endpoints. For the 7-day bladder diary, the entire 7-day duration need not be included in the entire visit window for it to be assigned to that visit e.g. if a patient has start date of the 7-day bladder diary on Day 61, then the 7th day would fall on Day 67, and would be assigned to Week 6 diary data.

If multiple unscheduled visits occur within a single visit, then the unscheduled visit closest to the target day of the visit window will be used in the analysis. If there is a tie, the later unscheduled visit will be used in the analysis. Similarly, if there are both scheduled and unscheduled visits prior to Treatment 1 then the last assessment prior to the Treatment 1 will be used as baseline in analysis of efficacy endpoints.

Statistical Analysis Plan

Version: Final v2.0

September-2018

Ipsen Protocol No. D-FR-52120-222

000000146259

Date of Issue: 21-

Covance Study ID:

Table 1 Definition of Visit Windows

Visit	Target Day of Visit ^a	Acceptable visit window mITT/PP analyses
Screening	Day -30	NA
Treatment visit of DBPC cycle	Day 1	NA
Week 2	Day 15	Days 8 to 22 (Day 15±7 days)
Week 6	Day 43	Days 23 to 63 (Day 43±20 days)
Week 12	Day 85	Days 64 to 106 (Day 85±21 days)
Week 24	Day 169	Days 107 to 211 (Day 169-62 days and +42 days)
Week 36	Day 253	Days 212 to 295 (Day 253-41 days and +42days)
Routine visit every 12 weeks until retreatment occurs or EOS	Day x + 84	Day x-41 days and Day x +42days)
End of Study^b (Week 104)	Day X	Day X±14 days
Retreatment Assessment Visit		Within 14 days of request
Retreatment Visit of treatment cycle 2 ^c	Day 1	Within 14 days of confirmed eligibility.
Week 2	Day 15	Days 8 to 22 (Day 15±7 days)
Week 6	Day 43	Days 23 to 63 (Day 43±20 days)
Week 12	Day 85	Days 64 to 106 (Day 85±21 days)
Week 24	Day 169	Days 107 to 211 (Day 169-62 days and +42 days)
Week 36	Day 253	Days 212 to 295 (Day 253-41 days and +42days)
Routine visit every 12 weeks until retreatment occurs or end of study	Day x + 84	Day x-41 days and Day x +42days)
End of Study^b (Week 104 to Week 116)	Day X	Day X ±14 days

^a Relative to the date of the first IMP administration (Day 1) of DBPC Cycle

^b The EOS visit will occur at Week 104 for subjects who had their most recent IMP administration at Week 92 or earlier.

^c The visit window from treatment cycle 3, 4, 5, etc. is the same as treatment cycle 2.

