- g Bladder diary device to be returned when subject completes study (e.g. in the event of screen failure, EOS Visit, Early Withdrawal Visit, etc.). Site should check if bladder diary has been commenced at least 8 days prior to visit. If not commenced then site should contact subject to remind subject (and/or caregiver) to commence collecting bladder diary data. Electronic bladder diary data may be reviewed by the site prior to the visit (recommended, to check if bladder diary is fully completed).
- h At the Retreatment Visit, vital signs will be recorded before and at least 30 minutes after treatment administration. In addition, blood pressure and heart rate will be monitored during the entire treatment procedure in subjects with spinal cord injury with lesions above the T6 level. See [Sections 8.4](#) and [6.2.4](#).
- i Visit window and timing relative to most recent Retreatment Visit
- j Telephone Visits may be conducted as clinic visits, if required in the investigator's opinion.
- k The EOS Visit will occur at Week 104 for subjects who had their most recent IMP administration at Week 92 or earlier. The EOS Visit will occur at the same time as the Week 12 post-retreatment Visit for subjects who had their most recent study retreatment after Week 92.

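### SAP 6.1 contradicts itself on the reference date for retreatment-cycle visit windows: Table 1 restarts at Day 1, but footnote a and the Day 1 definition count from the first injection

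*SAP*

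**What the plan says.** SAP 6.1 opens with a single reference date: "Day 1 is defined as the day of the first IMP administration". The one formula for later days uses it: "Relative days after Day 1 are calculated as (assessment date - Day 1 date) + 1". Section 6.1 defines no Day 1 for a treatment cycle.

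Table 1 then lists target days and windows, first for the double-blind placebo-controlled (DBPC) cycle and then for retreatment. The retreatment block begins with the row "Retreatment Visit of treatment cycle 2", whose target is Day 1. The Week 2, 6, 12, 24 and 36 rows follow with the same target days and windows as in the DBPC cycle. Footnote c carries these windows to cycles 3, 4, 5 and later.

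Footnote a is attached to the header of the target-day column, so it covers both blocks. It reads "Relative to the date of the first IMP administration (Day 1) of DBPC Cycle".

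The windows are a fallback. Analyses generally use nominal visits, and 6.1 adds: "Only if the data is missing, the unscheduled visits (or early withdrawal visit) within the visit window will be used in analysis of efficacy endpoints". If several unscheduled visits compete, the one closest to the target day is taken.

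For visit scheduling, Protocol 5.1, Table 5, footnote i uses another anchor: "Visit window and timing relative to most recent Retreatment Visit".

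**The concern.** The retreatment rows have two incompatible reference dates. The row structure says that the count restarts at each retreatment. The footnote and the text say that it runs from the first injection. A programmer who applies the footnote and the formula as written will compute study days, compare them with windows that make sense only as cycle days, and put substitute assessments in the wrong week.

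Retreatment efficacy is a secondary objective, and it is summarised by Dysport cycle. Dysport Cycle 1 (SAP 7.1) pools subjects given Dysport on Day 1, for whom the footnote is right, with placebo subjects' first Dysport treatment, for whom it is wrong. By plan, 55 + 55 = 110 of 330 subjects start on placebo. Every later Dysport cycle consists only of retreatment data. A literal reading would therefore use two different rules within one summary of Dysport Cycle 1.

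**Working it through.** **Inputs.** Target days and tolerances: SAP 6.1, Table 1. Day formula: SAP 6.1. Minimum gap between treatments: SAP 2.2, which allows a request from 12 weeks onward but lists more than 84 days as a retreatment criterion, so both are carried. Scheduling tolerances of ±3, ±3 and ±7 days for Weeks 2, 6 and 12: Protocol 5.1, Table 5.

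**Step 1: reproduce the plan's windows.** Target day = 7 × week + 1. Window = target day minus and plus the stated tolerance.

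| Visit | Target day | Window |
|---|---|---|
| Week 2 | 15 | 15 − 7 = 8 to 15 + 7 = 22 |
| Week 6 | 43 | 43 − 20 = 23 to 43 + 20 = 63 |
| Week 12 | 85 | 85 − 21 = 64 to 85 + 21 = 106 |
| Week 24 | 169 | 169 − 62 = 107 to 169 + 42 = 211 |
| Week 36 | 253 | 253 − 41 = 212 to 253 + 42 = 295 |

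All five agree with Table 1. The windows are not in question; their origin is.

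**Step 2: apply footnote a literally to the retreatment rows.**

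- Earliest cycle 2 treatment: study Day 84 + 1 = 85 (gap of at least 84 days) or 85 + 1 = 86 (gap of more than 84 days).
- The Week 2 window ends on Day 22 and the Week 6 window on Day 63. Both end before Day 85, so neither can hold a post-retreatment assessment in any cycle.
- The Week 12 window (Days 64 to 106) can hold at most the first 106 − 85 + 1 = 22 days of cycle 2 (21 days if retreatment is on Day 86). Cycle 3 cannot start before Day 2 × 84 + 1 = 169 (or 2 × 85 + 1 = 171), so from then on this window is empty too.
- For the earliest retreatment, the true cycle 2 Week 2 target falls on study Day 85 + 14 = 99 (or 100), inside the literal Week 12 window. The true Week 6 target falls on Day 85 + 42 = 127 (or 128), inside the literal Week 24 window.
- The literal reading also puts the cycle 2 Retreatment Visit on study Day 1, the day of the first injection. The minimum gap makes that impossible.

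**Step 3: an example that reaches the fallback rule.** A subject is retreated on study Day 169, misses the scheduled Week 6 visit, and has an early-withdrawal visit on cycle Day 50.

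- Study day of that visit: 169 + 49 = 218.
- Counted from the first injection: Day 218 lies in Days 212 to 295, so Week 36.
- Counted from the retreatment: Day 50 lies in Days 23 to 63, so Week 6.

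**Step 4: check the per-cycle anchor.** With Day 1 as the Retreatment Visit, the scheduling windows are 15 ± 3 = 12 to 18, 43 ± 3 = 40 to 46 and 85 ± 7 = 78 to 92. Each lies inside its analysis window (8 to 22, 23 to 63, 64 to 106). No window is empty by construction.

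**The case against.** The strongest reply is that the intent is clear and the table itself supplies it. Table 1 restarts at Day 1. SAP 2.2 repeats Week 2 (Day 15) and Week 6 (Day 43) after each retreatment. SAP 7.7.1 refers to a Day 1 for each Dysport cycle. Protocol Tables 3 and 5 label the Retreatment Visit as Day 1 of the treatment cycle. A careful programmer would notice that the literal reading is impossible. SAP 2.2 also refers to Appendix V for retreatment visits and SAP 3.2 to Appendix II for endpoint definitions. Neither appendix is in the public text, and either may define a day within the cycle.

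Most of this stands as evidence of intent. It does not remove the contradiction. The protocol footnote governs when visits are scheduled, and SAP 7.7.1 assigns adverse events to cycles. Neither sets the efficacy windows, which in the available text appear only in Table 1 under footnote a.

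The reply does defeat two stronger readings. A reader might infer that the SAP consistently counts retreatment cycles from the first injection. It does not, because the restarted Day 1 row contradicts that. A reader might also infer that the retreatment Week 2 and Week 6 analyses would have no data. They would have data, because scheduled visits enter under their nominal label whichever anchor is used.

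**Conclusion.** The contradiction is real and minor. Footnote a and the Day 1 definition are right for the DBPC cycle and wrong for the retreatment rows.

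The effect is confined to subjects in a retreatment cycle who lack data at a scheduled visit and have an unscheduled or early-withdrawal assessment that could replace it, and to the choice among several such assessments. The documents give no rate for this, so the number of affected values cannot be estimated.

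The output concerned is descriptive. SAP 7.6.6 limits treatment comparisons to the DBPC cycle. The line plots of least-squares means for Dysport cycles in SAP 7.6.3 could draw on the same values, but no comparison is planned from them. The log-rank test in Dysport cycles (SAP 7.6.6.4) uses time between treatments and does not depend on these windows. The primary and hierarchical endpoints are all at Week 6 of the DBPC cycle. The documents therefore do not support any inference that the main efficacy conclusions are at risk.

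This rests on two assumptions: that nominal visits are used first, as 6.1 states, and that the unseen appendices do not already define a cycle Day 1. If they do, 6.1 still needs to agree with them. Lowest severity.

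**What to change.** In SAP 6.1:

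1. Define cycle Day 1 as the date of the IMP administration that starts the cycle, and compute relative days from it for retreatment cycles.
2. Limit footnote a to the DBPC rows and the Week 104 end-of-study timing.
3. Add a footnote stating that the retreatment rows are relative to the Retreatment Visit (Day 1) of that cycle.

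The cost is a few lines of SAP text before database lock. No data collection, visit schedule, window width or design element changes.
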